6.3. Study Components

6.3.1. Phone call screening

The phone call screening will take place after participants have received the participant information. During the phone call screening process, potential participants will receive a short overview of the study and have a chance to raise questions. Once all questions have been answered, several key factors will be assessed to determine participants' eligibility by both the inclusion and exclusion criteria. Additionally, more comprehensive information will be gathered that is required for a smooth execution of the upcoming experiment.

1. Date of birth, including age, year, and month, but excluding the specific day.
2. Gender. Female Male Diverse Do not want to answer
3. Body weight in kg.
4. Height in m.
5. Healthy in general? Yes No
6. Any heart or vascular disease¹? Yes No
7. Take any medication²? Yes No
 - 7.1. If yes: Has any change in the intake³ in the last 3 months? Yes No
 - 7.2. If so, which ones, how often, since when and in what dosage?

¹ e.g. high blood pressure, heart failure, diabetes, ...

² e.g. painkillers, beta-blockers, thyroid medication, insulin, ADHD medication

³ dosage, frequency

8. Drink alcohol? Yes No
- 8.1. If so, how many units⁴ per week?
9. Take drugs? Yes No
10. For female participants: pregnant or breastfeeding? Yes No
11. Hours of work each week.
12. Did you have cataract surgery? Yes No
13. Have you been diagnosed with any eye disease? Yes No
14. Have you been diagnosed with any psychological disorder? Yes No
15. Do you have sleep problems? Yes No
16. Involved in shift work? Yes No
17. Wearing specially-filtered glasses? Yes No
18. Do you possess a smartphone? Yes No

Once participants are eligible based on the phone call screening, they will be invited for an initial visit at the University Hospital to sign the informed consent form, perform the eye examination, fill out questionnaires, and provide them with the wearable sensors and instruct them on how to complete the smartphone-based self-report forms over the data collection period.

6.3.2 Eye examination

For the eye examination, participants pass different stations on day 1:

1) Objective refraction

Participants sit in front of the autorefractor and an automated assessment of the refraction (sphere, cylinder, axis) is performed.

2) Testing Visual acuity (distance visual acuity)

sc (sine correctione)

Firstly, visual acuity is tested “uncorrected”, which is without glasses or contact lenses. Participants are positioned in a well-lit area in the standard distance from the visual acuity chart (with Landolt rings). The testing distance is typically 6 meters but it may vary, for example in smaller spaces. Here, mirrors can be used to achieve the required distance. The participant is instructed to cover one eye with the hand or an eye patch, and thereafter are asked to read the Landolt rings on the chart. The smallest line they can read correctly is recorded. The process is repeated with the other eye covered.

ccs (cum correctione sine)

The above-mentioned procedure for testing sc visual acuity is repeated, however with the participant’s own glasses (if applicable). Each eye is tested separately.

⁴ glasses

cc (cum correctione)

Participants are comfortably seated and positioned correctly in front of the phoropter. The height of the phoropter is aligned with the participant's eyes. The phoropter is set to its default position, with the lenses set to zero (no correction). Participants look at the visual acuity chart and different lenses are presented in order to find the lens combination that brings the best visual acuity. In this way best subjective spherical and cylindrical refraction are determined and documented for each eye. Values are compared to objective refraction and checked for plausibility.

3) Slit lamp examination

Participants are seated comfortably in front of the slit lamp. Height and position of the slit lamp are adjusted to participant's eyes. Pupils are not dilated with mydriatic eyedrops. The eyes are examined starting with the anterior segment. Especially the lens is investigated for its transparency and any signs of cataracts. Lens opacities are documented concerning the *lens opacities classification system III (LOCS III)*.

For posterior segment examination, additional lenses are used (90D) with the slit lamp to view the posterior segment of the eye. Any opacities of vitreous or floaters are recorded and retina, optic disc, macula and retinal vessels are inspected. All findings are documented and any abnormalities are evaluated for potential exclusion criteria.

4) OCT (Optical coherence tomography) examination of the retina

Participants are positioned in front of the OCT machine. Chin rest and forehead strap are adjusted so that the participant's head is stable and comfortable. The participant is asked to look straight ahead at the fixation target inside the machine. The focus of the OCT machine is adjusted until a clear image of the retina is visible on the screen. The image is captured and screened for any artifacts or distortions and is repeated if necessary.

5) Foveal reflectance analyzer

Participants will be seated with both forehead and chin supported. They will be instructed to look straight forward onto a bright white spot. The macular pigment reflectometer will record the difference between the light entering and leaving the eye across the visual spectrum. The participant will not notice any of this. Spectral analysis of the reflected light provides an adequate estimate of the yellowing of the intra-ocular lens.

6.3.3 Questionnaires

At the beginning of the study on day 1, participants will complete established questionnaires characterizing their typical behaviour and personality traits that may be relevant to better understand their light exposure and impacts thereof in daily life. These questionnaires will be implemented using the tool SoSci Survey and can be filled out with any device connected to the internet. The full list of questionnaires can be found in Table 1.

Table 1. List of questionnaires included in the study.

Questionnaire	Reference
Pittsburgh Sleep Quality Index (PSQI)	(Buysse et al., 1991)
Light Exposure Behaviour Assessment (LEBA)	(Siraji et al., 2022)
Munich Chronotype Questionnaire (MCU)	(Roenneberg et al., 2003)
BFI-K	(Rammstedt & John, 2005)
Subjective Vitality Scales (trait)	(Bertrams et al., 2020)
Satisfaction with Life Scale	(Diener et al., 1985)
Sensorische Verarbeitungssensitivität	(Satow, 2022)
Assessment of Sleep Environment (ASE) questionnaire	(Grandner et al., 2022)

6.3.4 Smartphone-based ambulatory assessment

The ambulatory assessment will be conducted via the m-Path app installed on the participants' own smartphones. The app is available for Android and iOS smartphones. It will prompt participants to fill out a short questionnaire six times per day by sending a push-notification. And participants will be asked to take pictures of every food or drink (except of water) and upload these pictures through the m-Path app. Data from the assessments is saved encrypted on a secure GDPR-compliant server in the EU and will be matched to the other collected data using a pseudonymized alpha-numeric code.

Table 2. Measures applied in the ambulatory assessment phase.

All beeps		References
Affective well-being	MOOD-zoom + extra items??	
Vitality	Subjective Vitality Scales (state)	(Bertrams et al., 2020)
Alertness	Karolinska Sleepiness Scale	(Akerstedt & Gillberg, 1990)
Daily Experiences	Stressor Occurrence	
	Uplift Occurrence	
Current Situation	Place	
	Activity	
	Social contact	
	Light sources	
	Perception of current light	(M. G. Figueiro et al., 2021)
Morning only		
Sleep parameters	CONSENSUS sleep diary	(Carney et al., 2012)
Sleep quality	Adapted PROMIS sleep disturbance short form	
Evening only		
Cognitive Function	2-back task	As already implemented in m-Path
Health	Self-Rated Health	
	Physical Symptoms	(Larsen & Kasimatis, 1991)

6.4 Measurement devices

All measurements within the framework of the research project are non-invasive, except for placing a continuous glucose monitor on the non-dominant forearm of participants from day 1 of the data collection period onwards.

Table 3 shows the different types and respective resolutions of the recorded data.

The continuous glucose monitor and the light sensor will be worn throughout the 12 days of the study, while the thermal skin sensors and the ambulatory blood pressure device will only be worn on day 11 and 12, between 08:30 and 17:00 h respectively.

Table 3. Data collected, methods and resolution.

Data	Unit	Device name	Frequency
Skin temperature	°C	iButtons	1 min
Interstitial glucose	mmol/L	Abbott Freestyle Pro IQ	15 min
Illuminance	Lux Melanopic EDI	Actlumus	1 min
Blood pressure	mmHg	ECGpro Holter-RR USB	15 min

6.4.1 Actlumus wearable light sensor

Participants will wear a light logger around the neck like a pendant to log daily light exposure levels. The light logger is only worn during the day and taken off at night, or when participants get in contact with water (e.g. showering or swimming). We will be using the ActLumus by Condor Instruments, which is an actimeter with integrated light logger. The logger estimates melanopic EDI and photopic lux through several light channels. The logger is very lightweight (12-31 g) and can be clipped to the collar, cloth or worn around the neck or clipped onto glasses to measure light at eye-level. Data will be read locally using a cable and transferred to our computers (no cloud or external server involved) and analysed with a locally installed software from Condor Instruments called ActStudio.

Fig.2. Actlumus wearable light-logger

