
1. Background

Within a day, the Earth rotates once around its own axis, causing predictable changes in light conditions throughout the day. In this context, humans have developed the ability to synchronize their physiological processes to a period length of around 24 hours, adapting to these recurring fluctuations. Our ambient light hence has a major influence on our physiology and psychology depending on the time of day. However, over the last century our relationship to light has drastically changed: our current “indoor society” spends about 90% of awake time indoors exposed to lower light intensities (e.g. up to 300 lux for typical electric office lighting) than outside in natural daylight (e.g. up to 100,000 lux on a sunny day), along with excessive exposure to artificial light during the evening beyond sunset. Yet, studies on the impact of daytime light exposure patterns are limited (Fleury et al., 2020). A chronic lack of daylight in combination with excessive light in the evening is increasingly being considered as a risk factor in the aging society's rising incidence of cardiovascular, metabolic, and psychological disorders. For example, experiencing darker days and brighter nights was associated with a higher risk for the onset of several psychological disorders such as depression or psychosis (Burns et al., 2023). In terms of short-term effects on potential mediating mechanisms, Harmsen et al. previously showed that bright light during office hours induced mostly favorable acute effects on glucose control and thermoregulation in older insulin-resistant volunteers compared to dim light (Harmsen et al., 2022) and that natural office lighting through windows improved glucose control in older type 2 diabetes patients (Harmsen et al., 2022). Similarly, when workers were exposed to higher levels of light during their workday, they reported increased vitality and lower depressive symptoms (Mariana G. Figueiro et al., 2017; Nagare et al., 2021). However, to date, there is only limited data on how light exposure patterns differ across the lifespan (Scheuermaier et al., 2010) and how aging may affect the influence of light on our physiology and psychology. First findings indicate that younger and older adults show different emotional effects of exposure to blue light (Sletten et al., 2009), but these differences have so far not been addressed in daily life.

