6.5 Flowchart and Schedule

After a person expressed interest in participation, researchers will reply by sending the information letter and consent form via email. Subsequently, researchers will schedule a phone call during which they will provide a brief overview of the key aspects of the experiment and address any questions or concerns which participants may have. Additionally, this phone call will serve as an opportunity to evaluate participants' eligibility based on the inclusion and exclusion criteria (see 6.3.1. phone call screening).

Following the phone call and scheduling the participation days, participants will sign the informed consent form during the first visit at the University Hospital.

On day 1, each participant will undergo an eye examination and thereafter starts wearing the wearable sensors and receives instructions on how to complete the smartphone-based self-report forms are provided. After the ambulatory assessment period in participants' everyday life (days 2-10), participants will spend the 11th and 12th day in a controlled office room environment from 08:30 to 17:00 h. Between day 11 and 12, participants will leave controlled conditions from 17:00 h on day 11 to 08:30 h on day 12.

Throughout these 12 days, the sensors continuously record data until they are removed at the end of day 12. Flowchart 1 illustrates this 12-day study period.

[figure not shown]

Fig.6.: Flowchart of chronological events of participants enrolment in the study.

7 Risks

Overall, the study ensures that participants are exposed to conditions within the naturally occurring limits of daily life. We do not expect any risks from participating in the ambulatory assessment with previous research showing high acceptability and no noteworthy reactivity to measurement in participants' behavior. Nevertheless, on day 11 and 12 participants may be exposed to light conditions that could be perceived as uncomfortable compared to their preferences.

Blood pressure measurements will be performed on day 11 and 12 by means of an automatic inflatable cuff. These measurements might feel a bit uncomfortable, but do not induce negative health effects. After wearing the continuous glucose monitor for 12 days, skin irritation can occur from where the sensor wire is inserted.

The eye examinations bring no special risks for participants. Individuals might feel dazzled for a few seconds after the slitlamp examination, especially after retinoscopy.

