8.3 Descriptive statistics

Statistical analysis will be performed using the statistical computer programs SPSS for Mac OS (version 25, IBM) and R Studio for Windows. Descriptive statistics will be reported for all data parameters and will be reported as minimum, maximum, mean, standard deviation (SD) and intraindividual standard deviation (iSD) for data assessed in daily life, and/or standard error of the mean (SEM). As a measure of dispersion, SD will be used for descriptive statistics of the assessed data, while the SEM will additionally be reported for the results of the primary and secondary outcomes.

In case of non-normality, values will either be transformed using log transformation or non-parametric tests will be used. In addition, Pearson correlation coefficients will be computed to correlate parameter values. The unpaired Students t-test will be used to compare outcome measures between the young and old group. Due to the randomized cross-over design, to compare outcomes between the bright and dim office light condition irrespective of age (secondary outcome), a paired t-test will be conducted. Differences will be considered statistically significant when tested two-sided $p < 0.05$. Missing values will not be replaced. We will apply a full information approach using all available data from all participants.

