8.4 Primary and secondary study parameters

As the primary hypothesis of this study is that younger and older individuals differ in their light exposure patterns in everyday life, the primary outcome of this study is melanopic equivalent daylight illuminance (M-EDI) quantified in lux by the Actlumus wearable light sensor. M-EDI may differ between groups with respect to overall daily levels, exposure levels at different times of day (work-day vs. weekend-day), and the difference in exposure levels between work-days and weekend-days. Therefore, M-EDI will be statistically analysed between groups in the following three ways:

1. Compare the area under the curve (AUC) of M-EDI from day 1 to day 8 between young and old (unpaired t-test)

2. Averaging exposure levels over work-days and weekend-days in 1-hour time intervals over 24 hours and compare the two average 24-hour M-EDI patterns between young and old (2-way repeated measures ANOVA, factor 1 (between-subjects) group, factor 2 (within-subjects) time)
3. Averaging the onset of M-EDI in the morning hours and the offset in the evening over work-days and weekend-days and calculate the difference in onset and offset between the averaged work-day and weekend-day between groups (unpaired t-test)

The secondary hypotheses are that light exposure patterns in everyday life are linked to daily metabolic, cardiovascular and psychological outcomes, and that this link is stronger in individuals displaying less degeneration of eye structures.

Accordingly, mixed effects regression analyses will be performed to assess the relationship between different aspects of daily light exposure (momentary M-EDI, average daily exposure level, onset/offset; independent variables) and each of the daily health parameters (metabolic, cardiovascular, psychological functioning, and sleep; dependent variables). To evaluate the role of the degree of eye degeneration, an interaction term between light exposure and eye degeneration will be added to the regression models.

9 Ethics

The study must be approved by the Ethics Committee of RWTH Aachen University. The study is carried out in accordance with the Declaration of Helsinki (the latest version, established in Fortaleza, Brazil, 2013) and the Law on Medical Research involving Human Beings (WMO) and the General Data Protection Regulation (GDPR or GDPR).

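### The light logger is off the body at night (Protocol 6.4.1), yet primary analysis 2 (8.4) compares M-EDI over 24 hourly cells, so its night cells cannot show participants' own exposure

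*Protocol*

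**What the plan says.** Section 6.4.1 sets the wear rule: "The light logger is only worn during the day and taken off at night". The logger also comes off for contact with water.

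Section 8.4 takes M-EDI from this logger as the primary outcome and lists three analyses. The second averages exposure "in 1-hour time intervals over 24 hours and compare the two average 24-hour M-EDI patterns between young and old", using a two-way repeated-measures ANOVA with group between and time within subjects. The first compares the area under the M-EDI curve from day 1 to day 8. The third compares the work-day to weekend-day difference in light onset and offset.

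Three other statements bear on the night hours:

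- Section 6.4: "The continuous glucose monitor and the light sensor will be worn throughout the 12 days of the study".
- Section 6.5: "Throughout these 12 days, the sensors continuously record data until they are removed at the end of day 12".
- Section 8.3: "Missing values will not be replaced. We will apply a full information approach using all available data from all participants". For non-normal data, 8.3 adds that "values will either be transformed using log transformation or non-parametric tests will be used".

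The protocol does not say where the logger lies at night, or whether night readings count as exposure, as zero or as missing.

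**The concern.** The time factor in a primary analysis covers hours in which the protocol's own wear rule keeps the sensor off the participant. Whatever fills those cells, it is not that person's exposure.

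The night part of the curve is easily over-read. The Background cites a study in which "experiencing darker days and brighter nights was associated with a higher risk", and 8.4 presents a full 24-hour pattern by age group. A group by time result driven by the night cells could be reported as an age difference in night-time light. It would in fact rest on very few participants or on where devices were put down. Under strict complete-case handling, analysis 2 could hardly be run at all.

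**Working it through.** **1. Inputs.** From the protocol: 30 participants per group (60 in all), 24 one-hour cells, logger off at night, missing values not replaced. The protocol gives no figure for hours off the body, so there is no stated figure to reproduce. I assume 7 to 9 hours per night.

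**2. Cells without on-body data.** 7/24 = 29%; 8/24 = 33%; 9/24 = 38%. So roughly a third of the time factor falls outside the wear rule.

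**3. Reading (a): off-body time is missing.** A classical repeated-measures ANOVA needs all 24 cells from each participant. Averaging over days helps only a little. The cells in the middle of the night are filled only if the latest removal on one day and the earliest refitting on another nearly meet.

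This was simulated with 400 trials per setting and n = 60, under these assumptions:

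- logger off 23:00–07:00, 23:30–06:30 or 22:30–07:30;
- SD of removal and refitting times 0.75 or 1.0 h between persons and 0.5 or 0.75 h from day to day;
- averages over 5 work-days or 2 weekend-days, the latter also shifted 1 h later;
- a cell counted as filled with at least 1 or at least 30 worn minutes on any day.

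| Quantity | Range over settings |
|---|---|
| Mean participants with all 24 cells | 0 to 0.6 of 60 |
| Largest number in any one simulated trial | 3 |
| Cells with data from fewer than 30 of 60 participants | 4.0 to 8.1 of 24 |
| Cells with data from fewer than 6 of 60 participants | 1.3 to 6.0 of 24 |

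The maximum is an extreme of random draws and can move by about one between runs; the mean is the steadier figure. The last two rows show that using partial data keeps participants in the model but does not supply night-time information.

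**4. Reading (b): the logger keeps recording.** All 24 cells are filled and the ANOVA runs. The night cells then hold the light at the place of storage, which the protocol does not fix. Simulated with identical worn light in both groups (30 per group, Greenhouse–Geisser test), the group by time test on raw lux rejects in 2 to 4% of trials at the nominal 5%. The fault here is one of interpretation, not of false positives on the stated scale.

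**5. Does a window of worn hours solve it?** For illustration only, 08:00–22:00 has 14 cells. Under the assumptions in step 3, 96 to 100% of these cells are filled within a day type, but only 62 to 100% of participants have all of them. The window removes the main problem. A model that accepts some missing hours is still needed to keep everyone.

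**6. Analyses 1 and 3.** The area under the curve from day 1 to day 8 spans off-body nights. In analysis 3, fitting the device in the morning or removing it in the evening can look like light onset or offset. Both analyses need the same off-body rule.

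**The case against.** The strongest case on the other side has four parts.

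- **Non-wear rules belong in the SAP, which is not shown.** This is partly right: how minutes are flagged can be left there. But the protocol itself fixes both the day-only wear rule and the 24-hour grid of a primary analysis. A non-wear rule alone would lead straight to reading (a).
- **Listwise deletion is not the documented intent.** Section 8.3 speaks of a full information approach, and 6.5 suggests that recording continues. This stands as far as it goes: the complete-case count applies only if off-body time is set to missing and a classical ANOVA is used. However, 8.4 names that ANOVA, and neither route turns night cells into exposure.
- **A logger at the bedside approximates bedroom light.** It might, but no placement is specified.
- **Night light is not a named aim.** Correct. The aims in section 2 do not mention it, and the remark on brighter nights describes one cited study. This limits the harm; it does not remove the mismatch.

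A reader might also infer a large type I error. On a log scale, which 8.3 allows for non-normal data, different storage habits in the two groups could produce a spurious group by time effect. The protocol does not support a figure. It gives no off-body lux, no evidence that the groups store the device differently, and no rule for zeros. If off-body readings differ between groups by an assumed factor of 2, a plain log of strictly positive readings gives 41 to 70% rejection. With log10(x + 1), the same factor gives about 8%, 19%, 29% and 46% at off-body medians of 0.1, 0.5, 1 and 5 lux. If the groups do not differ in storage, plain-log rejection stays at 4 to 5%.

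**Conclusion.** Wrong as written. Sections 6.4.1 and 8.4 cannot both be followed and yield a 24-hour exposure pattern. That conclusion rests on the text alone and needs no simulation.

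The size depends on assumed wear times. With 7 to 9 hours off per night, 29 to 38% of the hourly cells lack on-body data. If these are treated as missing in a classical repeated-measures ANOVA, a mean of 0 to 0.6 of 60 participants remain, against the aim in 8.3 to use all available data.

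Three limits apply. Worn daytime cells are not affected, so analysis 2 is not worthless. Type I error is not inflated on raw lux, and no figure is claimed for the log scale. Sections 6.4 and 6.5 need not contradict 6.4.1: a device can be worn on every study day and go on recording while off the body. They do not say that this is meant.

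**What to change.** In 8.4, analysis 2:

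1. Replace the 24-hour span with a clock-time window that is the same for both groups and set without looking at M-EDI or group. It should cover the hours in which nearly all participants wear the device and keep as much of the evening as wear allows, because the Background stresses evening light.
2. Exclude off-body minutes, flagged from the logger's actimeter channel. The sleep diary serves as support only, since it is not a log of device removal.
3. Analyse group by hour with a linear mixed model, with correlation within participant, so that participants with some missing hours are kept, in line with 8.3.

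In analysis 1, apply the same off-body exclusion to the area under the curve and state how unequal worn time is handled. In analysis 3, do not count fitting or removing the device as light onset or offset.

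In 6.4, 6.4.1 and 6.5, reconcile the statements on wear and recording.

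The cost is wording and some programming, with no new data collection. The plan gives up any claim about night-time exposure and has less information at the edges of the waking day. The illustrative 08:00–22:00 window would leave out 1 to 3 of the assumed 15 to 17 worn hours (15 − 14 = 1; 17 − 14 = 3), which is why a window that reaches later into the evening is preferable if wear supports it.
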